The secondary objective of study is to profile the safety of topically applied Timoptic- XE® in the treatment of DFU. We will monitor serum levels of timolol post-application to determine the plasma concentration of timolol in relation to its systemic bioavailability. Timolol levels will be determined using reversed-phase ultraperformance liquid chromatography and UV detection. The primary safety outcome will be the measurement of timolol serum during the treatment phase.

The secondary safety outcomes will be the following: the mean changes from baseline in systolic and diastolic blood pressure in mmHg, the mean changes from baseline in heart rate in beats per minute, and the measurement of all the adverse events associated with the use of Timoptic-XE®.

INCLUSION CRITERIA:

1. Male or female subject of any race 18 years old or older
2. Lower extremity ulcer located anywhere on the foot up to the ankle:
 - a. Of more than 30 days duration and less than 2 years duration (medically documented)
 - b. Surface area between 0.5cm² and 20cm² (as measured with the Silhouette imaging system at randomization). The ulcer with largest surface area meeting inclusion criteria will be selected as index ulcer
 - c. If two ulcers present with the same surface area, the ulcer of the longest duration will be selected as index ulcer
3. Documented Ankle Brachial Index (ABI) between 0.8 and 1.2 on the study limb or toe pressure over 65mmHg within 3 months of screening phase
4. Documented biopsy report to rule out malignancy of ulcer of > 6 months duration

EXCLUSION CRITERIA*:

A subject will be excluded from the study if any of the following criteria are met:

1. Ulcer of non-diabetic etiology, such as venous, arterial and burn wounds
2. Index ulcer is less than 3 cm in distance from any other ulcer on the same extremity
3. There are greater than 3 ulcers on the study foot
4. Index ulcer presents with any of the following: cellulitis, osteomyelitis, exposed bone, tendon or fascia, purulent exudate or gangrene
5. Index ulcer shows evidence of infection (defined as a moderate or severe rating of all of the following clinical signs/symptoms: 1) increased warmth, 2) increased pain, 3) erythema, and 4) malodorous exudate at Screening or at Randomization (Visit 1), OR total organism count > 1 x 10⁵ colony forming units (CFU) from the screening visit study ulcer culture sample)

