1.1. STUDY FLOW CHART

Study Plan Schematic

Procedure	Screening Phase Visits 1-2 (Week 1-2)		Active Phase Visits 3-14 (Week 3-14) Including a 1st confirmatory visit if healed before 12 weeks of treatment		2nd Confirmatory Visit Prior to Follow-up Phase Visit 15 (Week 15)	Follow-up Phase Visits 16, 17, 18 & 19 (Week 19, 23, 27 & 31)			
	Visit 1 (Week 1)	Visit 2 (Week 2)	Visit 3 (Week 3) Randomization	Visits 4-14 (Week 4-14) Study Endpoint at Week 14*	Visit 15 (Week 15)	Visit 16 (Week 19)	Visit 17 (Week 23)	Visit 18 (Week 27)	Visit 19 (Week 31)
Inclusion/Exclusion Criteria	X	X	X						
Informed Consent/HIPAA document	X								

VR-36 Health Survey Questionnaire	X			X*					
Lower Extremity Functional Scale Outcome Questionnaire	X	X		X					X
Charlson-Comorbidity Index	X								
Physical Exam	X			X*					
EKG	X			X*					
Vital Signs	X	X	X	X	X	X	X	X	X
Ankle-Brachial Index/Duplex Scan	X	X							
Debrided Tissue for genetic analysis (Weeks,1-9)	X	X	X	X					
Bacterial, Fungal Infection and Malignancy Evaluation	X								
Laboratory evaluation (hematology, renal, and liver function)	X								
Vapometer Readings@ (@If healed, readings recorded from point of closure + 4 months)				X@	X	X	X	X	X
Blood Sample for Timolol assay/Inflammatory markers(weeks 4,8,12)	X			X†					
Ulcer Assessment	X	X	X	X	X	X	X	X	X
Debridement († if needed)	X	X	X	X	X†	X†	X†	X†	X†
Ulcer Photography and Area Measurement	X	X	X	X	X	X	X	X	X
Offloading device	X	X	X	X	X	X	X	X	X
Randomization			X						
SOC + Timoptic-XE@ or SOC + non biologically active gel (hydrogel as placebo medication)			X	X					

SOC			X	X	X	X	X	X	X
Concomitant Medications and Adverse Events	X	X	X	X	X	X	X	X	X

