- If ulcers heal sooner than 12 weeks, the subject will be assessed the following week for a confirmatory visit, followed another week later by a 2nd confirmatory visit. Ulcer healing is defined by 100% epithelialization as determined by the clinician. The subject with healed ulcer will also return for follow-up visits Weeks 19, 23, 27 & 31 (visits 16, 17, 18 and 19).
 - Vapometer recordings will be collected on visits corresponding to weeks 19, 23, 27, and 31 on the newly healed ulcer site, 5 cm away from healed ulcer site. Readings on the contralateral side will also be marked and taken and recorded. **5 recordings for each site will be taken and the average will be documented.

NOTE: if ulceration remains open after the 12th week of application – then will switch back to standard of care and the subject will be followed monthly until completion of the study.

Blood samples will be taken on each subject on weeks 4, 8 and 12 to determine serum Timolol level. We do not anticipate blood levels in our patients to be higher than those seen in patients who receive Timoptic XE® gel for ocular indication (normal range: 0.3-0.5 ng/ml). We will terminate study on patients in whom Timolol level is 0.7 ng/ml or higher.

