Please read and follow carefully ALL the instructions at home DAILY:

1. Keep your dressing clean and dry at all times. When bathing, wrap the entire dressing with two large garbage bags and seal with surgical tape provided. DO NOT tighten the tape so it cuts blood flow. Do your best to avoid direct water contact with the wrapped foot.
2. Change your dressing once a day using specific materials provided to you by your doctor.
3. Apply the exact number of drops of the medication, as instructed by your doctor.
4. Cover the wound with Adaptic/Mepitel, sterile gauze and secure with paper tape (or kerlix wrap and tape).

Thank you for your cooperation.

Provider instructions:

1. Please review the instructions with the patient. Please ensure the patient understands the instructions and is capable of providing home care.
2. Do not forget to order relevant supplies.
3. Secondary dressings include use of Adaptic/Mepitel, gauze (or kerlix wrap), and tape placed by the clinician. Remember: Additional absorptive dressings may be used if there is excessive drainage.
4. Dressings should be changed daily per protocol instructions above.

11. APPENDIX 5 –Veterans Rand-36 (VR-36) Health Survey

Please see attachment in IRBNet, titled, “VR-36 Health Questionnaire”

12. APPENDIX 6 –Lower Extremity Functional Scale

The Lower Extremity Functional Scale

We are interested in knowing whether you are having any difficulty at all with the activities listed below because of your lower limb problem for which you are currently seeking attention. Please provide an answer for each activity.

Today, *do you or would you* have any difficulty at all with:

Activities	Extreme Difficulty or Unable to Perform Activity	Quite a Bit of Difficulty	Moderate Difficulty	A Little Bit of Difficulty	No Difficulty
1 Any of your usual work, housework, or school activities.					
2 Your usual hobbies, re creative or sporting activities.					
3 Getting into or out of the bath.					
4 Walking between rooms.					

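### Serum timolol, the primary safety outcome and the trigger for ending participation, is sampled at no set interval after the daily application, and the protocol does not require the application time to be recorded

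*Combined protocol and SAP*

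**What the plan says.** The Protocol Summary (Study Objectives) makes the level the leading safety measure: "The primary safety outcome will be the measurement of timolol serum during the treatment phase". The list of safety endpoints repeats this. The stated purpose, in the Protocol Summary and again in Section 2, is: "We will monitor serum levels of timolol post-application to determine the plasma concentration of timolol in relation to its systemic bioavailability".

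The on-treatment draws are set by week only. Section 4.3.3 reads: "Blood samples will be taken on each subject on weeks 4, 8 and 12 to determine serum Timolol level". The row of the Study Flow Chart reads "Blood Sample for Timolol assay/Inflammatory markers(weeks 4,8,12" and adds no clock time or interval.

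Section 4.3.3 expects levels no higher than with ocular use ("normal range: 0.3-0.5 ng/ml") and then gives the rule: "We will terminate study on patients in whom Timolol level is 0.7 ng/ml or higher".

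Treatment is daily for up to 12 weeks. Section 4.3.3 lists application of treatment among the weekly visit procedures. Appendix 4 covers application at home: "Apply the exact number of drops of the medication, as instructed by your doctor". It gives no time of day and no instruction for visit days.

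The Analyses part of Section 6 plans a two-way ANOVA relating timolol level to healing, with no mention of time since application.

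**The concern.** A drug level can be interpreted only if one knows how long after the dose it was taken. Here one limit and one reference range are applied to samples that, with daily application, can fall anywhere from about 0 to 24 h after the last dose.

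Three things are at stake:

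- **The rule.** A subject whose level passes 0.7 ng/ml at some point in the day may be sampled at another point and continue.
- **The safety summary.** Differences between subjects mix exposure with timing. A set of low values could be read as low systemic absorption when it partly reflects when blood was drawn.
- **The analysis of level against healing.** Variation in timing adds noise to the explanatory variable, and times that were not recorded cannot be recovered afterwards.

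**Working it through.** **1. Search for a timing rule.** The places where one could stand are these:

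| Place | What it fixes | What it leaves open |
|---|---|---|
| Protocol Summary and Section 2, objectives | Sample is taken after application | How long after |
| Study Flow Chart | Weeks 4, 8, 12 | Time of day, interval |
| Section 4.3.3, visit procedures | Treatment is applied at the visit | Whether blood is drawn before or after |
| Section 4.3.3, blood samples | Weeks, reference, limit | Interval; whether 0.3-0.5 and 0.7 are peak, trough or random levels |
| Appendix 4 | Daily home application | Time of day; what to do on a visit day |
| Section 6, Analyses | ANOVA of level and healing | Any use of time since application |

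None sets the interval or requires the application time to be recorded.

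**2. The plan's own figure.** The 0.7 ng/ml limit has no derivation in the documents, so there is nothing to reproduce. It is 0.7/0.5 = 1.4 times the top and 0.7/0.3 = 2.33 times the bottom of the stated ocular range.

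**3. Could levels reach 0.7?** Section 4.2 sets up to 3 drops (0.75 mg) a day. It gives the ocular dose as 0.25 mg/day, described as one drop in each eye, while the dose table equates one drop with 0.25 mg; those two statements need reconciling. If level is proportional to dose with equal absorption (an assumption):

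- against 1 ocular drop a day: 3 × (0.3 to 0.5) = 0.9 to 1.5 ng/ml;
- against 2 ocular drops a day: 1.5 × (0.3 to 0.5) = 0.45 to 0.75 ng/ml.

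On either count the limit lies within or below the range, so a level that triggers the rule is plausible.

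**4. How often could the rule miss?** Assumptions: first-order decline after the peak with half-life h (not in the documents; 2 to 24 h tried), no continuing absorption, and each draw independent and uniform over the 24 h after the peak.

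- Level at time t: peak × 2^(−t/h).
- Hours at or above 0.7: t* = h × log2(peak/0.7). For a peak of 1.4, t* = h; for 2.8, t* = 2h.
- Chance that one draw detects: p = min(1, t*/24).
- Chance that all three miss: (1 − p)³.

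| Half-life (h) | Peak 1.4: p | All three miss | Peak 2.8: p | All three miss |
|---|---|---|---|---|
| 2 | 0.083 | 0.77 | 0.167 | 0.58 |
| 4 | 0.167 | 0.58 | 0.333 | 0.30 |
| 6 | 0.25 | 0.42 | 0.50 | 0.125 |
| 12 | 0.50 | 0.125 | 1 | 0 |
| 24 | 1 | 0 | 1 | 0 |

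Independence helps detection. If a subject always applies and attends at the same hours, the three draws act as one. The miss probability for a peak of 1.4 is then 1 − p = 0.92, 0.83, 0.75, 0.50 and 0.

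**5. What can a reading just under 0.7 conceal?** At 12 h after the peak, it is compatible with a peak of 0.7 × 2^(12/h): 44.8, 5.6, 2.8, 1.4 and 0.99 ng/ml for h = 2, 4, 6, 12 and 24. At h = 24, even a draw 24 h after the peak conceals at most 0.7 × 2 = 1.4. A draw at the peak conceals nothing.

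**The case against.** The best reply is that the gap is real but its consequence is unknown. The documents give no half-life and no absorption profile. The product is a gel left under a dressing until the next daily change, so absorption may continue and flatten the curve. There are three draws, not one. With a half-life of 12 h, three random draws always catch a daily peak of 2.8 ng/ml, and they miss a peak of 1.4 only one time in eight. The limit may itself have been meant as a trough or random level, in which case a late sample is no mismatch. The stated aim of sampling after application, together with the in-clinic application, may mean that sites draw soon after a dose. Case report forms and laboratory procedures are not among the documents and may capture times. Other safeguards exist: vital signs at every visit, blood pressure and heart rate as secondary safety outcomes, exclusions 18-22, a data monitoring committee and a cardiology consultant.

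Most of this stands as a limit on size. A reader might infer that subjects far above the limit will pass, that samples will mostly be near trough, that the rule chiefly measures clock time, or that it fails in the unsafe direction. The documents support none of these, because each needs a decline rate, an order of draw and dose, or a peak-type limit that is not stated.

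The reply does not close the gap. That the rule can miss an excess needs only that levels fall between daily applications and that the limit is meant to cover the higher part of the day. That levels are not comparable needs only the first. The other safeguards do not make the level interpretable.

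**Conclusion.** The concern holds in a limited form. The protocol ties neither its primary safety outcome nor the 0.7 ng/ml rule to any interval after application. It leaves the visit-day order of draw and application open and does not require the application time to be recorded. The levels are therefore not comparable between subjects or with the reference range, and the rule can miss an excess.

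How often is not determinable from the documents. In the illustration for a daily peak at twice the limit, the chance that all three draws miss runs from 0.77 to 0 as the assumed half-life goes from 2 to 24 h. Those figures rest on first-order decline and random, independent draw times. Continuing absorption would lower them, and habitual timing could raise them. They show how much depends on an unstated quantity; they do not estimate the miss rate in this trial.

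**What to change.** In the Study Flow Chart and Section 4.3.3, the sponsor should set one interval between application and draw, the same for all subjects in both arms, at the three existing draws. Record the clock time of the last application and of the draw. Report levels with time since application, and carry that time into the planned analysis of serum level and healing in Section 6.

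Reconcile the objectives (Protocol Summary and Section 2), Section 4.3.3 and Appendix 4, so that the 0.3-0.5 ng/ml reference and the 0.7 ng/ml limit are stated to refer to the same kind of level as the sample. How a visit-day application relates to that day's home application is for the sponsor to reconcile. No dose, interval or threshold is proposed here.

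The cost is amended wording, two time fields, and possibly a wait in clinic at three visits. No extra samples or visits are needed.

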6. Index ulcer surface area has decreased or increased > 40% between Screening and at Randomization (Visit 1) as assessed by the Silhouette imaging system
7. Has medically documented history of Human Immunodeficiency Virus (HIV)
8. Has active malignancy on the study limb
9. Has uncontrolled diabetes mellitus as defined by glycosylated hemoglobin A1C > 12% within 3 months of screening
10. Has immunodeficiency as defined by serum IgG, IgA, and IgM less than one-half the lower limit of normal
11. Has severe protein malnutrition as defined by serum albumin < 2.5 g/dL

12. Has serum aspartate aminotransferase (AST, SGOT, GOT) or serum alanine aminotransferase (ALT, SGPT, GPT) levels greater than twice the upper limit of normal
13. Has fatigue, palpitations, dyspnea, and/or angina at rest
14. Has a medically documented or self-reported history, within the previous 12 months from date of Screening Visit, of alcohol or drug abuse, particularly methadone or heroin
15. Has received previous treatment with the following during the 60 days prior to Screening: Immunosuppressive agents, radiation, chemotherapy, growth factors (epidermal growth factor, tumor necrosis factor, transforming growth factor, platelet derived growth factor, etc.)
16. Has received previous treatment with the following during the 30 days prior to screening: the site of the study ulcer, split- or full-thickness skin graft at the site of the study ulcer, biologically-active (or engineered) cellular or acellular product(s) at the site of the study ulcer, investigational drug or device
17. Has been hospitalized for treatment of a diabetic foot ulcer within the previous 30 days from Screening
18. Has history of bradycardia (heart rate less than 60)
19. Has ESR>70mm/hr and CRP>100 mg/L at time of screening
20. Has medically documented history of hypotension/orthostatic hypotension and/or symptomatic hypotension (systolic blood pressure below 90 and diastolic blood pressure less than 60). (Note: There is no standard testing regimen protocol for orthostatic hypotension, even for patients starting on oral timolol, per the consultant Cardiologist, [name])
21. Currently taking asthma or COPD medications (as documented in chart)
22. Has a medically documented diagnosis of myasthenia gravis, untreated hyperthyroidism, , Type 2, Type 3 heart block, cardiogenic shock, overt cardiac failure
23. Female who is pregnant or refuses to use adequate contraceptive methods and is of childbearing age during the trial

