24. Prisoners, institutionalized individuals or vulnerable population
(The real-world group will not have any exclusion criteria related to timolol (criteria 18-22)

(*)Note: The exclusion criteria were modified compared to the original submission based on the recommendation from the DMC, which suggested that these criteria would significantly impair the enrollment. Those were also revised upon evaluation by the consultant Cardiologist, [name].

TREATMENT: Total duration of study per subject: Up to 31 weeks (Includes to 2 weeks of screening and up to 16 weeks until the end of the follow-up period). 12 weeks for the real-world group.

DURATION OF ADMINISTRATION: Daily application for 12 weeks (starting at Visit 3/Week 3).

STUDY DESIGN: This is a prospective, randomized, double blinded, controlled, and parallel-group study with 2 arms: β AR antagonist (SOC plus topically applied Timoptic-XE®) and control (standard of care (SOC) plus non-biologically active gel (hydrogel, Kendall®, placebo medication)).

EFFICACY ENDPOINTS:**PRIMARY EFFICACY OUTCOME**

1. Complete closure of ulcer by Visit 14/Week 14

SECONDARY EFFICACY OUTCOME

1. Complete closure of ulcer by Week 31
2. Percent difference change in size from the randomization visit to the endpoint visit (post 12 weeks)
3. Time to wound closure
4. Rate of ulcer healing
5. Change in transepidermal water loss of re-epithelialized wound after wound closure

SAFETY ENDPOINT:**PRIMARY SAFETY OUTCOME**

1. Timolol serum levels during the treatment phase

SECONDARY SAFETY OUTCOME

1. Mean changes from baseline in systolic and diastolic blood pressure in mmHg
2. Mean changes from baseline in heart rate in beats per minute
3. Adverse events associated with the use of timolol.

QUALITY OF LIFE ASSESSMENT: We will use ANCOVA to analyze the quality of life from the VR-36 Health Survey and the Lower Extremity Functional Scale Outcome Questionnaire.

DATA ANALYSIS:

The primary outcome is complete ulcer closure by Week 12 (end of the Active Phase) of the study and the rate of ulcer healing by the 12th week of care between the two arms.

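### Current timolol use by another route is neither excluded nor handled in the analysis, so in any such subject the primary safety outcome, serum timolol, cannot be attributed to the wound

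*Combined protocol and SAP*

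**What the plan says.** The Protocol Summary (Safety Endpoint) names "Timolol serum levels during the treatment phase" as the primary safety outcome. Section 2 explains its purpose: levels after application are to show how much drug becomes systemically available.

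Section 4.3.3 sets the sampling: "Blood samples will be taken on each subject on weeks 4, 8 and 12 to determine serum Timolol level". It gives the expectation, "We do not anticipate blood levels in our patients to be higher than those seen in patients who receive Timoptic XE® gel", and puts a figure on the levels used for comparison: "those seen in patients who receive Timoptic XE® gel for ocular indication (normal range: 0.3-0.5 ng/ml". It then sets an individual limit: "We will terminate study on patients in whom Timolol level is 0.7 ng/ml or higher". The limit refers to neither the source of the timolol nor a baseline value.

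The Study Flow Chart row "Blood Sample for Timolol assay/Inflammatory markers(weeks 4,8,12" is marked at Visit 1 as well as within Visits 4-14.

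On eligibility, the note after the exclusion criteria says "The real-world group will not have any exclusion criteria related to timolol (criteria 18-22". Within that group, the only bar on a current medicine is item 21: "Currently taking asthma or COPD medications (as documented in chart". Section 4.3.1 adds known allergy to the product. Concomitant medications are recorded from Visit 1, but no rule says what follows if one of them is timolol.

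The Data Analysis summary and section 6 plan a two-way ANOVA relating serum timolol to wound healing.

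**The concern.** A serum level measures absorption from the wound only if the wound is the sole source of the drug. The study drug is a marketed eye preparation, and the plan itself says what level its ocular users carry. A subject on timolol eye drops who meets the other criteria can be randomized, and the plan does not say how that subject's values are to be read.

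Three uses of the serum value are exposed: the primary safety summary, the ANOVA against healing, and the individual 0.7 ng/ml limit. In the first two, a Group B user adds a positive level that did not come from study treatment, and a Group A user adds a level that mixes two sources. In the third, a Group A user could be taken off study partly because of eye drops.

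**Working it through.** **Step 1. Is there a bar?** I read all 24 exclusion criteria, the inclusion criteria and section 4.3.1.
- Items 18-22, which the plan calls timolol-related, cover bradycardia, ESR/CRP, hypotension, asthma/COPD medicines and certain diagnoses.
- Items 15-16 list earlier treatments and name no beta-blocker. A routinely prescribed eye drop is not an investigational drug.
- Section 4.3.1 adds allergy only.

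None of these removes a current timolol user.

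**Step 2. Serum reading in Group B.** Inputs from section 4.3.3: ocular level 0.3-0.5 ng/ml; study level expected to be no higher than that range. The two figures cannot be derived from the documents and are taken as given.
- Group B, no other timolol: 0.
- Group B, eye drops: 0 + (0.3 to 0.5) = 0.3 to 0.5 ng/ml.
- Group A, no other timolol: expected no higher than 0.3 to 0.5 ng/ml.

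The second and third lines overlap, so the level alone does not separate a control subject on eye drops from a treated subject.

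**Step 3. Distance to the 0.7 ng/ml limit.** Assume the two sources add.
- Eye drops alone: 0.3/0.7 = 43% to 0.5/0.7 = 71% of the limit, so it is not reached.
- Room left for wound absorption: 0.7 - 0.5 = 0.2 to 0.7 - 0.3 = 0.4 ng/ml. A subject with no other timolol has the full 0.7.

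| Level from wound (ng/ml) | Total with eye drops (ng/ml) | Reaches 0.7? |
|---|---|---|
| 0.1 | 0.4-0.6 | no |
| 0.2 | 0.5-0.7 | only at the top of the ocular range |
| 0.3 | 0.6-0.8 | for part of the ocular range |
| 0.4 | 0.7-0.9 | across the whole ocular range |
| 0.5 | 0.8-1.0 | across the whole ocular range |

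Every wound level in the table lies within what the plan expects.

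**Step 4. Healing comparison, as a bound only.** The plan's sample size reproduces. For 20% against 63%, two-sided Fisher's exact test at 5%, exact power (the binomial probabilities of all tables with p ≤ 0.05, summed) is 79.5% at 23 per arm and 82.5% at 24, so 24 is the smallest number giving 80%.

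The share s of timolol users is not in the documents; I assume 2%, 5% and 10%. Case (a) supposes that control users heal at the timolol rate: 0.20(1 - s) + 0.63s. Case (b) supposes that every Group A user is terminated and counted as not healed: 0.63(1 - s).

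| s | (a) difference, power | (b) difference, power | both |
|---|---|---|---|
| 2% | 42.1 points, 80.6% | 41.7 points, 79.9% | 40.9 points, 77.8% |
| 5% | 40.9 points, 77.5% | 39.9 points, 75.7% | 37.7 points, 69.8% |
| 10% | 38.7 points, 72.0% | 36.7 points, 67.9% | 32.4 points, 54.6% |

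These are worst cases under invented shares. They limit the possible harm and are not evidence that it occurs.

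**The case against.** The strongest reply is that this may concern nobody. The share of timolol users is unknown and could be zero among 48 subjects. Concomitant medications are recorded and every subject is sampled, so a positive Group B value would show itself, and randomization balances users in expectation. That is fair as to size. But detection without a rule leaves the handling to be chosen after the data are seen, and balance between arms does not tell a reader where one subject's timolol came from.

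The exclusion criteria were also relaxed on the data monitoring committee's advice to protect enrolment. That stands as a reason to keep any new criterion narrow.

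Three stronger readings are tempting, and the documents do not support them.
- *Eye drops or tablets alone could end a subject's participation.* On the plan's figures ocular use peaks at 0.5 ng/ml. No serum level is given for oral timolol.
- *Most Group A users of eye drops would cross 0.7 ng/ml.* If both sources were independent and uniform on 0.3-0.5, the share below 0.7 would be (0.1²/2)/0.2² = 12.5%, and 87.5% would cross. But the plan gives that range as an upper expectation for the wound, not as a distribution. With a wound contribution of 0.1 or less, none would cross.
- *The treatment contrast is determined by non-study timolol.* Section 1 cites in vitro, animal and topical evidence. Nothing there shows that serum timolol from eye drops heals a foot ulcer. Even if one control user healed at 63% instead of 20%, the expected shift would be 0.43/24 = 1.8 points.

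**Conclusion.** The gap is real but narrow. In any ocular timolol user, the primary safety outcome and the serum-against-healing ANOVA are confounded, because the background level equals the plan's own upper expectation for the wound. In Group A such use cuts the room before 0.7 ng/ml from 0.7 to 0.2-0.4, so a wound level within expectation can reach the limit. This rests on the 0.3-0.5 ng/ml figure as stated and on the levels being additive.

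How many subjects are affected cannot be said from the documents; each one is 1/24 = 4.2% of an arm. An effect on the healing comparison is possible but not shown. This is a cheap improvement to the attribution of a safety outcome, not a threat to the primary efficacy analysis.

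**What to change.** 1. Add one eligibility line excluding current ophthalmic or oral timolol, checked against the concomitant-medication list already collected from Visit 1. Users of other beta-blockers stay eligible: they bring no timolol into the serum, and this respects the enrolment concern.
2. Reconcile the flow chart, which marks the blood sample at Visit 1, with section 4.3.3, which names weeks 4, 8 and 12 only. The row is shared with inflammatory markers, so the Visit 1 mark may not mean a timolol assay. Confirm that the Visit 1 sample is assayed for timolol as a baseline.
3. For any subject already enrolled on timolol, or who starts it during treatment, prespecify that the serum-timolol summaries and the ANOVA are reported with and without those subjects.
4. The sponsor and investigator should state how the 0.7 ng/ml rule applies when some of the timolol is not study drug. This review does not propose that rule.

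Cost: a short amendment, the loss of a few otherwise eligible subjects, and possibly one more baseline assay per subject. If enrolment has closed, item 1 no longer applies, but item 3 still can.
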